### **6.13 Privacy & Confidentiality**

Patient's personal health information will be kept confidential, unless release is required by law. The consent form should make note that representatives of the local REB and/or institution, the Canadian College of Naturopathic Medicine (CCNM) and/or their designee, as well as Health Canada may review original medical records.

Patients enrolled in the study will not be identified in any publications or presentations resulting from this study, unless permission is given by the patient. All case report forms and associated source documents will be kept in locked cabinets and all databases will be password protected – both will be kept for a period of 25 years. Case report forms will be shredded and databases will be destroyed at the end of this retention period.

[figure not shown]
A password-protected file will be maintained at each participating center and will contain patients' names and corresponding unique study identifiers, only of individuals they have enrolled at their site. A second separate password-protected database will be maintained at the Coordinating Center and will contain information gathered from the case report form with the unique study identifier from all participating centers. This information will not leave the Ottawa Hospital.

## 7.0. Sample Size Determination

The tables and graphs below demonstrate the means through which we can achieve much greater power to detect a real difference by increasing the sample size to a total of 640.

Assuming that one arm of the trial (intervention or placebo) sees a combined event rate of 5% for the primary outcome of recurrence and mortality and our total N = 640 (320 per arm) then we will be able to see a proportional difference as low 6 to 7% with a power of 80 to 90% respectively (Figure 1). The initial proposal was to see an absolute difference of 15% in recurrence and mortality given 80% power. The addition of 280 participants (80 from the substudy and an additional 200 from this request) will enable a much greater resolution for a smaller benefit which is also clinically relevant. Most importantly if there is a real benefit to be seen then we will be much less likely to miss it with an expanded trial population.

*Figure 1: Graph of power versus rate difference to detect for a reference rate of 5 %. [So: with a reference of  $p_1 = 5 \%$ , a difference  $p_2 - p_1 = 0.07$  or 7 % implies that  $p_2 = 12 \%$  and approximately 85% power] - 320 in each arm.*

[figure not shown]

The next graph (figure 2), demonstrates that if indeed the clinical difference due to the melatonin intervention causes a 15% absolute change (say from 20% to 5%) then with a sample size of 640

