**Protocol Amendment: March 6th 2013**

**Protocol Amendment: March 19th 2014**

**Protocol Amendment: December 8th 2014**

## 1. Background and Rationale

Lung cancer accounts for the greatest incidence of cancer mortality worldwide; more than colon, gastric, prostate and breast cancer combined, in men and women respectively [1]. According to a 2002 report by the International Agency for Research on Cancer, lung cancer was responsible for 1.18 million deaths yearly [2]. Non-small-cell lung cancers (NSCLC) comprises the vast majority of cases accounting for 80% of lung cancer diagnoses [3]. Surgical resection followed by adjuvant platinum-based chemotherapy remains the standard of care, offering the best chance for long-term care in patients with resectable disease who can tolerate surgery [4, 5]. Despite optimal therapy, however, loco-regional or systemic recurrence occurs in an unacceptably high proportion of patients, leading to mortality in the vast majority of those patients [6].

A recently validated prognostic index designed for NSCLC gives some measure of expected mortality in patients with this disease [3]. The patient's index is scored based on performance status, age, sex, histological type, and TNM staging. Using this index system and dividing the risk strata into five categories, the rates for 2-year mortality in each respective quintile are: 1st: 39%; 2nd: 72%; 3rd: 81%; 4th: 93%; and 5th: 96% [3]. Using the more standard International System for Staging Lung Cancer, 2-year survival based on initial diagnosis of clinical disease stage is: IA: 82%; IB: 59%; IIA: 57%; IIB: 43%; IIIA: 27%; IIIB: 15%; and IV: 10% [7].

[figure not shown]

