## 5. Eligibility Criteria

### 5.1 Inclusion Criteria

1. Adult males or females with a clinical diagnosis confirmed by pathology of Stage I, II, III, or IV primary NSCLC who are eligible and scheduled for surgical resection.
2. Willingness to adhere to randomized treatment.
3. Availability for follow-up schedule of visits.
4. Ability to answer self- and interviewer- administered questions in English or French, or have an appropriate person available to assist with translation.

5. Understand and sign a written informed consent form in English or French, or have an appropriate person available to assist with translation.
6. For the sub-study only, willingness to have additional blood taken for study purposes.
7. Verbal confirmation from females of childbearing age that they are not pregnant, or documented birth control method or menopause. Breastfeeding patients will not be included in this trial.

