## NSCLC Adjuvant melatonin RCT

[figure not shown]
we essentially have 100% power to detect this difference i.e. this difference will be incredibly unlikely to be missed due to chance.

*Figure 2: For group rates of 20 % and 5 %, power versus sample size per group for different null rate differences.*

In the third and final graph (Figure 3) if we see an event rate of 20% which is also possible in our population and there is a drop of only 5% we are actually powered to nearly 90% with a population of 640.

*Figure 3: For group rates of 20 % and 15 %, power versus sample size per group for different null rate differences.*

For the phase II sub-study, we are interested in exploring potential mechanisms through which melatonin may be exerting activity. An exploratory pilot analysis of 80 subjects will provide information on what is occurring physiologically and is powered to see a 30% significant shift in NK cell functional activity. In addition, with 40 patients in each group, the expected number with recurrence or mortality is expected to be approximately 16 subjects, allowing for comparison of the NK cell function and biologic markers amongst this subgroup, compared to those without recurrence for both the melatonin and the control groups.

Although sample size calculation represent only rough estimates of the true sample required [79], confidence intervals around the primary endpoint will provide strong inferences into how well powered the trial is. It should be noted that our proposed sample is much larger than any of the previously conducted melatonin/cancer trials for which a statistically significant reduction in mortality was found after only one year. Given the sample size we will accrue, we confidently anticipate that the trial is well powered to address the primary objective without undue use of time and resources. The addition of the mechanistic substudy and trial extension will greatly extend the impact of the trial and potential for strong results to lead to policy shifts and a change in pattern of clinical practice leading to better patient care.

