## 8. Statistical Analysis

The primary analysis will be performed using an ‘intention to treat’ analysis. Using this approach, patients will be included in the analysis according to the group to which they were randomized regardless of cross-over or compliance. Baseline characteristics of patients in the two treatment arms will be assessed using frequency distributions and univariate descriptive statistics including measures of central tendency and dispersion. As a complementary approach,

we will also conduct a treatment received as ‘per protocol’ analysis of the primary outcome measures. Baseline characteristics in the two treatment arms will be compared using univariate descriptive statistics.

The primary analysis of the composite outcome of two-year cancer recurrence and mortality will be conducted using an unadjusted chi-square test comparing the proportion of events in each of the two treatment groups. This will be translated into a relative risk (RR), relative risk reduction (RRR), absolute relative risk (ARR), and number needed to treat (NNT). In addition, a logistic regression procedure will be employed to adjust exacerbation proportions using covariates that are either clinically important prognostic risk factors or unbalanced at baseline.

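### Section 7's headline claim of 80 to 90% power for a 6 to 7 point difference rests on an unsourced 5% event rate that does not fit the protocol's own figures

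*Combined protocol and SAP*

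**What the plan says.** Section 7.0 (Sample Size Determination) opens with a scenario in which one arm, either melatonin or placebo, "sees a combined event rate of 5% for the primary outcome of recurrence and mortality". With "our total N = 640 (320 per arm"), it says the trial can see "a proportional difference as low 6 to 7% with a power of 80 to 90% respectively". The other arm is therefore at 11 to 12%. The legend to the section's Figure 1 gives a slightly different power for the 7-point case: "and approximately 85% power] - 320 in each arm". No source is cited for the 5%.

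Two further scenarios follow. One is 20% against 5%, with power described as essentially 100%. The other is 20% against 15%, introduced with "if we see an event rate of 20% which is also possible in our population" and credited with power close to 90%. The section then expects about 16 substudy patients, with 40 in each group, to recur or die.

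Elsewhere:
- Section 5.1 admits "Stage I, II, III, or IV primary NSCLC" scheduled for resection. Section 5.2 excludes anyone whose cancer cannot all be resected.
- Section 6.5 defines the primary outcome as recurrence and/or death within two years of starting the intervention.
- Section 1 gives two-year survival by clinical stage at diagnosis: "IA: 82%; IB: 59%; IIA: 57%; IIB: 43%; IIIA: 27%; IIIB: 15%; and IV: 10" (all percentages).
- Section 8 tests the primary outcome with an "unadjusted chi-square test comparing the proportion of events in each of the two treatment groups".

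**The concern.** The detectable difference for a fixed sample size depends on the event rate, because binomial variance is small near 5% and grows towards 50%. If the true control rate is well above the 11 to 12% that this scenario allows, 640 patients cannot resolve 6 to 7 points with the stated power.

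The figure is relied on. Section 7 justifies the added 280 participants by the finer resolution they bring and concludes that the trial is well powered. Section 14 says that, if melatonin proves ineffective, patients will have good evidence to stop taking it. That use of a null result needs a realistic statement of the benefit the trial could have missed.

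**Working it through.** **Inputs.** 320 per arm (Section 7). Chi-square comparison of two proportions (Section 8). Section 7 states neither alpha nor sidedness, so two-sided 5% is assumed (z = 1.96). No dropout is allowed for, as in Section 7.

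**Formula.** With d = |p1 − p2| and p̄ = (p1 + p2)/2:

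power = Φ[ (d − 1.96·√(2p̄(1 − p̄)/n)) / √((p1(1 − p1) + p2(1 − p2))/n) ]

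**Step 1: reproduce the plan.**
- 5% v 11%: p̄ = 0.08; standard errors 0.02145 (null) and 0.02132 (alternative). (0.06 − 1.96 × 0.02145)/0.02132 = 0.843, so power is 80.0%.
- 5% v 12%: p̄ = 0.085; standard errors 0.02205 and 0.02187. (0.07 − 1.96 × 0.02205)/0.02187 = 1.225, so power is 89.0%.

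The text's 80 to 90% is reproduced. The legend's approximate 85% for 5% v 12% is close to a continuity-corrected calculation (86.0%), which may explain why text and legend differ.

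**Step 2: what the protocol implies about the rate.**
- Substudy forecast in Section 7: 16/80 = 20% across both groups, or 16/40 = 40% if 16 is per group. The sentence gives no time horizon; two years is assumed.
- Section 1 table, mortality = 100 − survival: IA 18%, IB 41%, IIA 43%, IIB 57%, IIIA 73%, IIIB 85%, IV 90%. In the same patients, a composite of recurrence and death cannot be lower than mortality alone.
- Neither 5% nor 11 to 12% reaches the lowest of these. If 5% is taken as the melatonin arm, the relative risk would be 5/18 = 0.28 against an 18% control, or 5/20 = 0.25 against 20%. The NSCLC subgroup meta-analysis in Section 1 gives 0.68 (for one-year mortality); 0.68 × 18% = 12.2% and 0.68 × 20% = 13.6%.

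**Step 3: power at those rates.** Worked case, 20% v 14%: p̄ = 0.17; standard errors 0.02970 and 0.02960. (0.06 − 1.96 × 0.02970)/0.02960 = 0.061, so power is 52.4%.

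| Control rate | Basis | Power, 6 points | Power, 7 points | Smallest difference, 80% power | Smallest difference, 90% power |
|---|---|---|---|---|---|
| 18% | stage IA, deaths only | 56.6% | 71.1% | 7.7 points | 8.8 points |
| 20% | 16 of 80 | 52.4% | 66.5% | 8.1 points | 9.2 points |
| 40% | 16 of 40; close to stage IB deaths | 34.9% | 45.2% | 10.5 points | 12.1 points |

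**Step 4: the section's other scenarios.**
- 20% v 15%: p̄ = 0.175; standard errors 0.03004 and 0.02997. (0.05 − 1.96 × 0.03004)/0.02997 = −0.296, so power is 38.4%, against a stated figure close to 90%. A one-sided test gives 50.8%, and 640 per arm gives 65.4%. Power of 90% would need 1,212 per arm.
- 20% v 5%: above 99.9%, as stated. A 15-point reduction keeps at least 96.8% power at every stage-specific rate from 18% to 90%.

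**The case against.** The strongest reply is that the Section 1 table does not describe this trial's patients. It is by clinical stage at diagnosis and not limited to resection. The trial takes only patients whose cancer can all be resected, and the two-year clock starts with the intervention, at discharge or up to 60 days after surgery, so earlier deaths do not count. The stage IIIB and IV figures say little about such patients. This stands: the documents give no two-year rate for resected patients, and 18% is a strong indication, not proof. It does not remove the conflict with the substudy forecast, which is the protocol's own expectation for trial patients. Counting recurrence also pushes the composite upward.

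A second reply is that 5% is one conditional scenario, assignable to either arm, and that 20% also appears. That is correct, so it would be wrong to call 5% the sole planning rate. But the only small-difference scenario at 20% is 20% v 15%, which has about 38% power.

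A third is that Section 7 looks to confidence intervals around the primary endpoint to show how well powered the trial is. Those intervals will reflect observed rates whatever was planned. That limits the harm at the analysis stage but does not correct the stated justification.

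On the lower reading of the forecast the shortfall is modest, about 1 to 2 points. The 10.5-point figure needs a rate near 40%, which rests on the per-group reading or on the unrestricted table.

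**Conclusion.** The point holds as an unsupported planning assumption, not as an arithmetic slip in the 5% calculation. The claimed resolution of 6 to 7 points at 80 to 90% power is not delivered at the rates the protocol itself gives. Power for those differences is between 35% and 71% over control rates of 18% to 40%, and the smallest difference with 80% power is 7.7 to 10.5 points. A true benefit of 6 to 7 points would be missed about 29% to 65% of the time. These figures assume a two-sided 5% test, no dropout and a two-year horizon for the 16-event forecast.

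A reader might go further and infer that 5% is shown to be impossible for the enrolled population, or that the trial as a whole is underpowered. The documents support neither. The stage table is not restricted to resected patients, and the original 15-point target remains well powered. Nor do they show that a null result would be read as ruling out a 6 to 7 point benefit. They show only that the plan's stated resolution would invite that reading.

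**What to change.** In Section 7, replace the 5% reference with a supported two-year composite rate for the control arm. Enrolment began in 2007 (Section 6.3) and Section 15 already counts about 40 recurrences at Ottawa, so pooled, blinded events and stage counts are available. With 1:1 allocation, the control rate is the pooled rate plus half the assumed difference. Reconcile the result with the 16-event forecast, and say whether 16 is overall or per group and over what period.

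Then give detectable differences for 640 patients over control rates of about 18% to 40%: 7.7, 8.1 and 10.5 points at 18%, 20% and 40% for 80% power. State alpha and sidedness, correct the power for 20% v 15%, and bring the text and the Figure 1 legend into agreement on 5% v 12% if that scenario is kept for illustration.

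This is a rewrite of one section. Sample size, endpoint and analysis do not change. The cost is a less favourable stated detectable difference.

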## NSCLC Adjuvant melatonin RCT

[figure not shown]
we essentially have 100% power to detect this difference i.e. this difference will be incredibly unlikely to be missed due to chance.

*Figure 2: For group rates of 20 % and 5 %, power versus sample size per group for different null rate differences.*

In the third and final graph (Figure 3) if we see an event rate of 20% which is also possible in our population and there is a drop of only 5% we are actually powered to nearly 90% with a population of 640.

*Figure 3: For group rates of 20 % and 15 %, power versus sample size per group for different null rate differences.*

For the phase II sub-study, we are interested in exploring potential mechanisms through which melatonin may be exerting activity. An exploratory pilot analysis of 80 subjects will provide information on what is occurring physiologically and is powered to see a 30% significant shift in NK cell functional activity. In addition, with 40 patients in each group, the expected number with recurrence or mortality is expected to be approximately 16 subjects, allowing for comparison of the NK cell function and biologic markers amongst this subgroup, compared to those without recurrence for both the melatonin and the control groups.

Although sample size calculation represent only rough estimates of the true sample required [79], confidence intervals around the primary endpoint will provide strong inferences into how well powered the trial is. It should be noted that our proposed sample is much larger than any of the previously conducted melatonin/cancer trials for which a statistically significant reduction in mortality was found after only one year. Given the sample size we will accrue, we confidently anticipate that the trial is well powered to address the primary objective without undue use of time and resources. The addition of the mechanistic substudy and trial extension will greatly extend the impact of the trial and potential for strong results to lead to policy shifts and a change in pattern of clinical practice leading to better patient care.

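### Section 7.0 claims nearly 90% power for a drop from 20% to 15% with 640 patients; the planned chi-square test has about 38% at an assumed two-sided alpha of 0.05

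*Combined protocol and SAP*

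**What the plan says.** Section 7.0 illustrates the power of the enlarged trial with three scenarios.

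- **Figure 1.** With a 5% event rate in one arm and "our total N = 640 (320 per arm"), the text claims a "proportional difference as low 6 to 7% with a power of 80 to 90% respectively (Figure 1"). The figure's caption takes 5% against 12% as its example and ends "and approximately 85% power] - 320 in each arm".
- **Figure 2.** For 20% against 5%, power is said to be essentially 100%.
- **Figure 3.** For a 20% event rate, which the section calls possible in this population, the text says that if "there is a drop of only 5% we are actually powered to nearly 90% with a population of 640". The caption reads "For group rates of 20 % and 15 %, power versus sample size per group for different null rate differences", so the drop is five percentage points and not a relative 5%.

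The section concludes that "we confidently anticipate that the trial is well powered to address the primary objective". Section 8 makes the primary analysis of the two-year composite of recurrence and mortality an "unadjusted chi-square test comparing the proportion of events in each of the two treatment groups". Neither section states an alpha level, whether the test is one- or two-sided, whether a continuity correction applies, or any non-zero null difference for the primary comparison.

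**The concern.** A move from 20% to 15% is a small difference between proportions of this size, and 320 per arm is far from enough for 90% power. The section's own first scenario points the same way: with a 5% rate in one arm, where the variance is much smaller, it needs a six-point difference for 80% power. A five-point difference at a rate near 20% must have less power than that.

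The scenario is not remote. Section 7.0 expects about 16 patients with recurrence or death in the substudy of 40 per group. That is 16/80 = 20% if the 16 are a total, and 16/40 = 40% if they are per group. Neither is near 5%.

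At stake is the reading of a null result. Section 14 says that a finding of ineffectiveness would give patients good evidence to stop taking melatonin. A reader who believes the trial had nearly 90% power for a five-point drop would treat a non-significant result as strong evidence against a benefit of that size. The design cannot supply that evidence if the event rate is near 20%.

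**Working it through.** **Inputs.** Rates 20% and 15% (Section 7.0, Figure 3 text and caption); n = 320 per arm (Section 7.0); unadjusted chi-square on two proportions, null difference zero (Section 8). Alpha is not stated; two-sided 0.05 is assumed and varied below. No dropout is applied, as Section 7.0 gives no allowance; missing outcomes would lower the power.

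**Formula.** Power = Φ[(d − z × SE0) / SE1], where d is the difference in rates, p̄ their mean, SE0 = √(2p̄(1 − p̄)/n) and SE1 = √((p1(1 − p1) + p2(1 − p2))/n).

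**Step 1: the section's other figures, two-sided 0.05.**

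- 5% v 11%: SE0 = √(2 × 0.08 × 0.92/320) = 0.02145; SE1 = √((0.0475 + 0.0979)/320) = 0.02132. (0.06 − 1.96 × 0.02145)/0.02132 = 0.84, power 80.0% (text: 80%).
- 5% v 12%: SE0 = 0.02205, SE1 = 0.02187. (0.07 − 1.96 × 0.02205)/0.02187 = 1.22, power 89.0% (text: 90%; caption: about 85%). With a continuity correction it is 86.0%, but the corrected value for 5% v 11% is then 75.7%.
- 20% v 5%: power 99.99% (text: essentially 100%).

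The assumed alpha and the uncorrected test therefore fit the text for Figures 1 and 2.

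**Step 2: 20% v 15%.** SE0 = √(2 × 0.175 × 0.825/320) = 0.03004; SE1 = √((0.16 + 0.1275)/320) = 0.02997. (0.05 − 1.96 × 0.03004)/0.02997 = −0.296, power **38.4%**.

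**Step 3: other readings of 20% v 15%.**

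| Reading | Power |
|---|---|
| 320 per arm, two-sided 0.05, exact enumeration | 38.3% |
| 320 per arm, two-sided 0.05, continuity-corrected | 34.4% |
| 320 per arm, one-sided 0.05 | 50.8% |
| 640 per arm, two-sided 0.05 | 65.4% |
| 640 per arm, one-sided 0.05 | 76.1% |

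To reach 90% with 320 per arm, the critical value would have to be (0.05 − 1.2816 × 0.02997)/0.03004 = 0.386, a one-sided alpha of about 0.35.

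**Step 4: a possible source.** The Figure 3 caption mentions several null differences. If the null is shifted towards harm and tested at one-sided 0.025, four points gives 0.09/0.02997 − 1.96 = 1.04 (85%) and five points gives 0.10/0.02997 − 1.96 = 1.38 (92%). The figure is not available, so this is only a possible explanation. Such a curve would describe a non-inferiority test, which Section 8 does not plan.

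**Step 5: what 320 per arm can do from a 20% rate, two-sided 0.05.**

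- Detectable drop: 8.1 points at 80% power, 9.2 points at 90%.
- For scale only, 20% v 15% would need 906 per arm for 80% and 1,212 for 90%.
- If exactly 64 v 48 events were observed (20% v 15%): z = 0.05/0.03004 = 1.66, p = 0.096, 95% CI 5.0 ± 5.9, that is −0.9 to 10.9 points.
- If both arms showed 20%: half-width 1.96 × √(2 × 0.16/320) = 6.2 points, which still includes a five-point benefit. If both showed 5%: 1.96 × √(2 × 0.0475/320) = 3.4 points, which does not.

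**The case against.** The arithmetic is hard to contest; the objections concern weight and scope.

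- **Only an illustration.** This is one of three scenarios, and 640 was not derived from it. The total came from adding 280 participants to a trial first sized for a 15-point difference. That is true, and it is why the sample size need not change. But the statement is still used to support the conclusion that the trial is well powered, and it is wrong by about 50 percentage points.
- **The plan already hedges.** Section 7.0 calls sample-size calculations rough estimates and says that "confidence intervals around the primary endpoint will provide strong inferences into how well powered the trial is". That helps with interpretation after the event. It does not correct a false planning figure, and roughness does not explain 38% becoming 90%.
- **The alpha is assumed.** The exact replacement figure does depend on it. The conclusion does not: no conventional alpha comes close to 90% with 320 per arm, and two-sided 0.05 fits the section's other text figures.
- **Figure 3 cannot be seen.** This stands against any claim about where the number came from. It does not protect the sentence, whose inputs are all printed.
- **The Figure 1 mismatch is small.** Agreed. The 90% in the text is within rounding of 89.0%, and the caption's 85% is near the continuity-corrected 86.0%. It is a tidying point.
- **The six-to-seven-point claim is already conditioned on a 5% rate.** Correct; it needs no further limit.

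**Conclusion.** The concern holds. For 20% against 15% with 320 per arm, the planned test has about 38% power, not nearly 90%, on the assumption of a two-sided 0.05 uncorrected chi-square and complete outcome data. It has about 51% at one-sided 0.05. Misreading 640 as the number per arm, alone or together with a one-sided 0.05 test, does not rescue the claim. The chance of missing a true five-point drop is about six in ten (about five in ten at one-sided 0.05), against the one in ten that the text implies. The text for Figures 1 and 2 is sound. How far a non-significant result limits the plausible benefit will depend on the event rates observed: at around 20% in both arms a five-point benefit would remain possible.

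**What to change.** Amend Section 7.0 as follows.

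1. State the alpha, the sidedness, and whether the chi-square is continuity-corrected, and carry the same choice into Section 8.
2. Replace the Figure 3 power with about 38% (two-sided 0.05, uncorrected), or with the value for the alpha adopted.
3. Make sure that any power quoted from Figure 3 is for a null difference of zero; otherwise remove the figure.
4. Add that from a 20% rate, 320 per arm detects a drop of about 8.1 points with 80% power and 9.2 points with 90%.
5. Bring the Figure 1 caption into line with the text; the uncorrected test gives about 89% for 5% against 12%.
6. Say that a non-significant result will be interpreted from its confidence interval at the observed event rates.

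This costs wording only: no more patients, no new data, and no change to the sample size, endpoint or test. The price is a less favourable power statement for the 20% scenario.
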